11.3.1 Serious and Unanticipated Adverse Device Effects (UADE)

An unanticipated adverse device effect is defined as “any serious adverse effect on health or safety or any life-threatening problem or death caused by, or associated with, a device if that effect, problem, or death was not previously identified in nature, severity, or degree of incidence in the investigational plan, or any other unanticipated serious problem associated with a device that relates to the rights, safety or welfare of subjects.”

11.3.1.1 Sponsor Investigator Responsibilities

The Sponsor-Investigator will promptly review documented adverse effects and abnormal test findings to determine 1) if the abnormal test finding should be classified as an adverse effect; 2) if there is a reasonable possibility that the adverse effect was caused by the investigational device or, if applicable, other study treatment or diagnostic product(s); and 3) if the adverse effect meets the criteria for a *serious adverse effect*.

In accordance with 21 CFR Part 812.150(a)(1) and (b)(1), the sponsor shall promptly report the results of an evaluation of any serious and unanticipated adverse device effect to FDA as soon as possible, but not later than 10 working days after the sponsor investigator first receives notice of the effect. The UADE should also be reported to the University of Michigan IRB according to the IRB reporting guidelines. Complications and non-serious or anticipated adverse events should be documented and tabulated but need not be submitted by the sponsor investigator to the FDA as individual reports. All vision threatening adverse events should also be reported to FDA, and the reviewing IRB, and all participating investigators in the same manner as reporting a serious and unanticipated adverse device effect.

11.3.2 Non-serious or Anticipated Adverse Events

Non-serious or anticipated adverse events and complications should be documented on the CRFs and tabulated for reporting as required according to the FDA and IRB reporting guidelines.

11.4 Monitoring

11.4.1 Medical Monitor

An independent Medical Monitor will be appointed to review each Serious Adverse Event. Any Serious Adverse Events will be reported to [name], the sponsor of the study, who will in turn notify the Medical Monitor. The Medical Monitor will review the event, request any additional data if necessary, and make a determination regarding expectedness and relatedness. Also, the Medical Monitor will determine if this safety data increases the risks to subjects on the trial. All non-serious adverse events will also be reviewed by the Medical Monitor on a quarterly basis.

[name] will be responsible for reporting the events to the IRB and the FDA as appropriate. The Medical Monitor review will be maintained in the study records.

The Medical Monitor may meet in person or through a teleconference with other individuals with clinical expertise as needed.

11.4.2 Clinical Trial Monitor

To assure adequate protection of the rights of human subjects, per 21 CFR §812.40, 812.43 and 812.46, this study will be monitored by the University of Michigan Institute of Clinical and health research (MICHR). Routine monitoring will be scheduled at appropriate intervals, with more frequent visits occurring at the beginning of the study. A site activation visit will take place, followed by routine monitoring visits. Additional visits can be scheduled at the request of the Sponsor-Investigator.

The established monitoring plan will ensure the quality and integrity of the data throughout the study conduct to verify adherence to the protocol, completeness and accuracy of study data and samples collected, dispensing and inventory of the device, and compliance with regulations.

11.5 Source Documents / Case Report Forms

Adequate records will be maintained for the study including subject medical and surgical records, signed ICFs, and device use records. All original source documentation will remain at the investigative site. Study data that are stored at the investigator site in any electronic medical records system, including measurements that are obtained electronically, will be printed and retained in the study files.

All study data will be recorded onto CRFs designed for the study. Copies of the CRFs will be retained with the Sponsor-investigator's study files.

11.6 Deviation from the Protocol

The sponsor investigator will not intentionally deviate from the protocol without prior IRB approval, unless such deviation is necessary to manage a medical or ocular urgency or emergency. The sponsor investigator will notify the IRB of any protocol deviation to protect the

life, vision, or physical well-being of a subject in an emergency. Such notice shall be given as soon as possible, but in no event any later than 5 working days after the emergency occurred. All other revisions and/or amendments to the protocol that affect subject treatment, study outcome, or subject safety should be submitted in writing to the IRB for approval prior to implementation. The sponsor investigator should maintain a record of all protocol deviations showing the dates of, and the reason for, each protocol deviation.

Changes that affect the scientific soundness of the study or the rights, safety, or welfare of human subjects may also require FDA approval, in addition to sponsor and IRB approval, prior to implementation. The sponsor investigator will obtain such approvals, if required, according to the regulations found in 21 CFR 812.35.

Appendix A: Glasgow Benefit Inventory (Adapted)

THE GLASGOW HEALTH STATUS QUESTIONNAIRES MANUAL, 1998

Introduction

The overall success of any medical or surgical intervention cannot be obtained from measures of technical success alone and changes in patient quality of life resulting from the intervention must also be considered. Another area of interest is the state quality of life patients have due to their health problem.

While there are existing measures of health status and patient satisfaction which can be used to assess state quality of life and changes brought about by ORL interventions; none of these measures were generated specifically for the ORL department. Therefore, limitations such as length, administration style and insensitivity to nonacute disorders, like those generally seen in an ORL clinic, mean that the evaluations generated from these measures for ORL interventions are not as sensitive as when these measures are used to assess other interventions. It was, therefore, decided to generate two health status questionnaires, a state questionnaire and a change questionnaire, which would be specifically sensitive to ORL health problems and interventions but also generalizable across different ORL health problems and interventions. The questions are independent of any specific intervention/health condition and the subject of the questions remains constant. Each of the questions addresses an aspect of health-related quality of life which is not dependent on the disease of interest or the context of the intervention. However, the text is altered for each question to allow focusing on to the intervention or health condition of interest to improve sensitivity. The questions are then generic in nature but referenced to a temporal event (intervention) in the GBI or condition in the GHSI.

The change questionnaire, called the Glasgow Benefit Inventory (GBI), measures the change in health status produced by surgical interventions. For this measure, the definition of health status is the general perception of well-being, including total psychological, social and physical well-being. Given that maximal sensitivity to change was critical, it was decided to ask directly about the change in health status resulting from surgery, rather than take pre- and post- operative measures and subtracting one from the other. The paper, (pages 18 to 31), shows the findings of a study investigating the sensitivity of the GBI to the change in health status resulting from 5 different ORL interventions.

The state measure we developed is called the Glasgow Health Status Inventory, (GHSI) which measures the effect of a health problem on the quality of life of a person and allows cross-

comparison among many health conditions, among different health interventions, and among demographic and cultural subgroups.

The GBI is a post-intervention questionnaire which assesses the interventions effects on the health status of the patients. The GHSI can be used at any point in time and measures the general quality of life the person experiences and how health problems affect this. While the GBI is maximally sensitive to a change in health status brought about by a specific event (e.g. an operation), the GHSI gives a general measure of the health status of the person at any specific time.

GBI - Glasgow Benefit Inventory

The GBI contains 18 change in health status questions which assess how the intervention has altered the quality of life of the person. The GBI is easily adapted to be used for different interventions. Before use, the GBI must be adapted so that the intervention of interest is specified. This is done by replacing the words in italics (*operation/intervention*) in each question into the intervention of interest. See the examples below. GBI was developed and validated as a measure of patient health for otorhinolaryngological procedures. It has been validated for use following oculoplastic procedures, including DCR^{19,20,21,22,23}, ptosis^{24,25}, ectropion and entropion surgery²⁶, and botulinum toxin for blepharospasm²⁷.

Example of all-purpose GBI question:

Since your *operation/intervention, have you found it easier or harder to deal with company?**

Examples of focused GBI questions:

Since your operation, have you found it easier or harder to deal with company?

Since your received your hearing aid, have you found it easier or harder to deal with company?

Since your speech therapy, have you found it easier or harder to deal with company?

Does the condition of your nose affect how you deal with company?

Scoring

The response to each question is based on a five-point Likert scale ranging from a large deterioration in health status through to a large improvement in health status, (see example below).

1. Has the result of the operation/intervention* affected the things you do?				
Much worse	A little or somewhat worse	No change	A little or somewhat better	Much better
1	2	3	4	5

To help control for response bias, half of the questions have the answers ranging from a large improvement to a large deterioration while the other half range the other way. The GBI questionnaire is scored into a total score and also 3 subscales:- a general subscale, (12 questions), a social support subscale, (3 questions), and a physical health subscale, (3 questions). All these scores range from -100 to +100.

Score all questions so that a score of 1 is given to the answer with the worst change in health status and 5 to the answer with the best change in health status.

Total Score

- Sum all the responses (Qu. 1-18)
- Divide by 18 (to obtain an average response score)
- Subtract 3 from the average response score
- Multiply by 50.

General Subscale Score

- Sum 12 of the responses (Qu. 1,2,3,4,5,6,9,10,14,16,17 and 18)
- Divide by 12 (to obtain an average response score)
- Subtract 3 from the average response score
- Multiply by 50.

Social Support Score

- Sum 3 of the responses (Qu. 7,11,15)
- Divide by 3(to obtain an average response score)
- Subtract 3 from the average response score
- Multiply by 50.

Physical Health Score

- Sum 3 of the responses (Qu. 8,12,13)
- Divide by 3(to obtain an average response score)
- Subtract 3 from the average response score
- Multiply by 50.

The GBI questionnaire (Modified for this study):

1. Has the result of the tear duct surgery affected the things you do?

Much worse	A little or somewhat worse	No change	A little or somewhat better	Much better
1	2	3	4	5

2. Have the results of the tear duct surgery made your overall life better or worse?

Much better	A little or somewhat better	No change	A little or somewhat worse	Much worse
5	4	3	2	1

3. Since your tear duct surgery, have you felt more or less optimistic about the future?

Much more optimistic	More optimistic	No change	Less optimistic	Much less optimistic
5	4	3	2	1

4. Since your tear duct surgery, do you feel more or less embarrassed when with a group of people?

Much more embarrassed	More embarrassed	No change	Less embarrassed	Much less embarrassed
1	2	3	4	5

5. Since your tear duct surgery, do you have more or less self-confidence?

Much more self-confidence	More self-confidence	No change	Less self-confidence	Much less self-confidence
5	4	3	2	1

6. Since your tear duct surgery, have you found it easier or harder to deal with company?

Much easier 5	Easier 4	No change 3	Harder 2	Much harder 1
------------------	-------------	----------------	-------------	------------------

7. Since your tear duct surgery, do you feel that you have more or less support from your friends?

Much more support 5	More support 4	No change 3	Less support 2	Much less support 1
------------------------	-------------------	----------------	-------------------	------------------------

8. Have you been to your family doctor, for any reason, more or less often, since your tear duct surgery?

Much more often 1	More often 2	No change 3	Less often 4	Much less often 5
----------------------	-----------------	----------------	-----------------	----------------------

9. Since your tear duct surgery, do you feel more or less confident about job opportunities?

Much more confident 5	More confident 4	No change 3	Less confident 2	Much less confident 1
--------------------------	---------------------	----------------	---------------------	--------------------------

10. Since your tear duct surgery, do you feel more or less self-conscious?

Much more self-conscious 1	More self-conscious 2	No change 3	Less self-conscious 4	Much less self-conscious 5
-------------------------------	--------------------------	----------------	--------------------------	-------------------------------

11. Since your tear duct surgery, are there more or fewer people who really care about you?

Many more people 5	More people 4	No change 3	Fewer people 2	Many fewer people 1
-----------------------	------------------	----------------	-------------------	------------------------

12. Since you had the tear duct surgery, do you catch colds or infections more or less often?

Much more often 1	More often 2	No change 3	Less often 4	Much less often 5
----------------------	-----------------	----------------	-----------------	----------------------

13. Have you had to take more or less medicine for any reason, since your tear duct surgery?

Much more medicine 1	More medicine 2	No change 3	Less medicine 4	Much less medicine 5
-------------------------	--------------------	----------------	--------------------	-------------------------

14. Since your tear duct surgery, do you feel better or worse about yourself?

Much better 5	Better 4	No change 3	Worse 2	Much worse 1
------------------	-------------	----------------	------------	-----------------

15. Since your tear duct surgery, do you feel that you have had more or less support from your family?

Much more support 5	More support 4	No change 3	Less support 2	Much less support 1
------------------------	-------------------	----------------	-------------------	------------------------

16. Since your tear duct surgery, are you more or less inconvenienced by your tearing problem?

Much more inconvenienced 1	More inconvenienced 2	No change 3	Less inconvenienced 4	Much less inconvenienced 5
-------------------------------	--------------------------	----------------	--------------------------	-------------------------------

17. Since your tear duct surgery, have you been able to participate in more or fewer social activities?

Many more activities 5	More activities 4	No change 3	Fewer activities 2	Many fewer activities 1
---------------------------	----------------------	----------------	-----------------------	----------------------------

18. Since your tear duct surgery, have you been more or less inclined to withdraw from social situations?

Much more inclined 1	More inclined 2	No change 3	Less inclined 4	Much less inclined 5
-------------------------	--------------------	----------------	--------------------	-------------------------

GLASGOW BENEFITS INVENTORY REFERENCES

- 1 McDowell I, Newell C. Measuring health: A guide to rating scales and questionnaires. Oxford:Oxford University Press.
- 2 Bowling A. Measuring health. A review of quality of life measurement scales. Milton Keynes:Open University Press.
- 3 Wilkin D, Hallam L, Doggett M-A. Measures of need and outcome for primary health care. Oxford:Oxford University Press.

Appendix B: Lac-Q Questionnaire

The Lac-Q Questionnaire:

The Lac-Q questionnaire, published in 2011, is a patient symptom questionnaire developed for lacrimal drainage surgery.¹⁻² The questionnaire contains two scores, one is specific for eye-symptoms, and the other assesses the social impact of symptoms. (see below)

Lac-Q - The Lacrimal Symptom Questionnaire Name: _____ Number: _____ Date: _____

Social and lifestyle impact of tear duct problem

Which of these five statements is true about the tear duct problem overall in the last eight weeks?
 Please tick the box next to any true statement.

- Friends or family have commented about the watery eye problem.
- The watery eye problem has caused embarrassment in company.
- The watery / sticky eye problem has interfered with everyday activity, for example (underline each that applies):
 Reading .. Driving .. Wearing make-up
 Wearing glasses .. Hobbies
 Other activity (specify):
- The vision is sometimes blurred because of the watery / sticky eye problem.
- Medical attendance: visit to the family doctor's surgery, or the hospital eye clinic, because of tear duct problem.

(Scoring: score one point for each box ticked, maximum score =5)

Total score for social impact:

Problems with each eye separately

For each of the four problems (watery eye, pain, sticky eye or swelling), put a tick in the box next to the statement which best describes the situation over the last eight weeks.
 Use the left hand column for the left eye, and the right hand column for the right eye.

	Left	Right
• Watery eye		
No watery eye problem		
The eye waters occasionally, mainly outdoors		
Troublesome watering of the eye, indoors and outdoors, some days		
Troublesome watering of the eye most days		
Troublesome watering of the eye every day		
• Pain in or around the eye; soreness of eyelids		
No pain		
Some pain or soreness, but has not sought medical advice or treatment		
Pain or soreness, has used prescription eyedrops		
Painful and swollen (lacrimal abscess), requiring antibiotics or surgical drainage		
• Sticky eye		
No problem with sticky eye		
The eye is sometimes sticky in the mornings		
The eye is sticky every day in the mornings		
The eye has sticky or mucous discharge throughout the day		
There is infected discharge leaking through the skin of the lower eyelid (fistula)		
• Swelling or lump at the medial canthus (mucocoele)		
No swelling or lump		
Swelling present, but only intermittently		
Swelling present all the time		

(Scoring: use numbers in central column) **Total scores for each eye:**

Lac-Q score (sum of three total scores):

Scores for the filled in questionnaire:

Social and lifestyle impact score (sum of social impact questions)

Left eye symptom score (sum of “left” column of symptom questions)

Right eye symptom score (sum of “right” column of symptom questions)

Lac-Q score (sum of all three total scores above)

LAC-Q QUESTIONNAIRE REFERENCES

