9.0 STUDY PROCEDURES

Subjects who elect to participate in this study will complete the study as outlined below. Subjects will be randomly assigned to the experimental vs. control stents using a randomized block design with 1:1 allocation to treatment and control. Stents will be provided to the surgical team on the day of surgery by the Study Coordinator. Surgical team, recruitment staff, and scheduling staff will be masked to treatment assignment until day of surgery. All tests and measurements should be obtained in accordance with the procedures specified in this protocol. If it is not possible to perform a measurement or examination due to the individual eye's specific ocular pathology, the reason for not performing the test or measurement should be documented on the source documents.

The investigator may designate one or more surgeon sub-investigators at his/her investigative site. A surgeon sub-investigator may evaluate subjects for the study and perform the Slit Stent II lacrimal stent intubation. Surgeon sub-investigators will be listed on all applicable investigator regulatory documents (including the delegation of responsibilities log) and will complete all sponsor-required training for the study.

For the pre-op and all post op study visits, the Lac-Q Questionnaire will be administered by an interviewer, and the interviewer will record the subject's responses directly onto the corresponding questionnaire CRFs or source documents and calculate the Lac-Q score. For post op visits, the Lac-Q Questionnaire will be given prior to other questionnaires.

For the two post-op study visits, the Quality of Life (QOL) questionnaire (Glasgow Benefit Inventory (GBI)- see Appendix A) and the Patient Stent Tolerance and Irritation Assessment (see Appendix C) will be administered by an interviewer, in this order, and the interviewer will record the subject's responses directly onto the corresponding questionnaire CRFs or source documents and calculate the GBI score.

When multiple questionnaires are given at the same visit, the order shall always be: 1) Lac-Q, 2) GBI QOL, and 3) Patient Stent Tolerance and Irritation Assessment.

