9.3.3 Postoperative Care

Written postoperative instructions will be given to each subject and reviewed prior to discharge. The following postoperative eye drops will be prescribed for the following minimum times:¹

- An antibiotic-steroid combination eye drop (e.g. Tobramycin-Dexamethasone or Neomycin-Polymyxin-Dexamethasone) placed 4 times daily for 2 weeks, then twice daily for 2 weeks, then once daily for at least 2 weeks or until stent removal, as determined by the surgeon.

Additional medications including, but not limited to, erythromycin ointment and bacitracin ointment will be used at the discretion of the operating surgeon. All postoperative eye drop usage will be recorded on the source documents and on the CRFs. Other prescription or nonprescription medications, including pain medications, may be taken as needed throughout the study.

9.4 ***Follow-Up Visits (Day 1 phone call, Day 5-14 Postoperatively, Day 30-60 phone call, Day 30-120 Postoperatively, Month 5-7 Postoperatively)***

A study flow chart summarizing the follow-up examination schedule and required procedures to be performed at each study visit is provided in **Appendix D**. All subjects will be seen for a 1st post-operative visit 5-14 days after the DCR with intubation, for a 2nd post-operative visit at 30-120 days after intubation, and for a final visit at month 5-7 postoperatively, with the exact timing dependent on patient findings and surgeon discretion. Unscheduled visits may be completed at the investigator's discretion or as medically necessary.

During the Day 1 and Day 30-60 phone assessments, the patient will be asked about any

¹ An alternative antibiotic or anti-inflammatory drug and dosage regimen may be used to conform with clinic or hospital formulary or prescribing requirements, with sponsor approval. An example would be neomycin-polymyxin-dexametasone eye drop (i.e. "Maxitrol").

postoperative swelling or pain or other adverse effects. If the patient reports any symptoms that would require a follow-up visit, we will ask the patient to return to the University of Michigan if possible. If this is not possible due to transportation issues, we will have them return to their referring ophthalmologist.

The following procedures will be performed **at the day 5-14 and day 30-120 post-operative visits** unless noted otherwise.

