- **Documentation of interim medical, ocular, and medication histories** since previous visit. The ocular history should capture any changes in the study eye since the previous visit; and, any relevant changes to the fellow eye that are necessary to evaluate an adverse event or anomaly in the study eye. The medication history should capture any changes in prescribed medications or routinely taken non-prescription medication since the previous visit.
- **Subjective reports of tearing-** we will capture the subject's report of their tearing symptoms since the surgery procedure
- **Corrected distance visual acuity** - Corrected visual acuity is measured in each eye by the ETDRS chart at 3 meters using the manifest refraction obtained at the previous visit. If there is a 2-line or more reduction in visual acuity from the last corrected visual acuity, a repeat manifest refraction in each eye will be performed.
- **Intraocular pressure-** Intraocular pressure measurement is measured by the ICare tonometry method, performed after visual acuity measurement had been completed.
- **Slit lamp biomicroscopy** (including conjunctiva and cornea), with use of fluorescein- Slit lamp biomicroscopy should include a complete survey of the conjunctiva and cornea, and of the tear lake. The Oxford scheme will be used to grade corneal and conjunctival staining. The tear lake is measured using a slit lamp by narrowing the slit and shortening it to 1 mm or 0.2 mm, placing the slit light beam on the inferior lid margin tear lake, and using the beam to measure the vertical height of the fluid between the lid margin and the location of the top of the tear lake on the conjunctiva or cornea.
- **Visual inspection of stent integrity and slit positioning-** External and slit lamp exam of the medial canthal area and the medial commissure. The presence of the lacrimal stent within the medial commissure, between the puncta, will be documented as (1) present, slit in fissure, (2) present, slit not in fissure, or (3) not present.
- **Lac-Q questionnaire (Appendix B)**
- **Glasgow Benefit Inventory Questionnaire (Appendix A).**
- **Patient Stent Tolerance and Irritation Assessment (Appendix C)**
 - **The 3 questionnaires will always be given in the same order: 1) Lac-Q, 2) GBI, and 3) Stent Tolerance Assessment.**
- **Other diagnostic tests-** Jones I, Jones II or lacrimal irrigation at investigator's discretion

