10.0 DATA ANALYSIS AND STATISTICAL CONSIDERATIONS

A detailed statistical analysis plan (SAP) will be developed for analysis of all data for this study. Required analyses and target endpoints that will be included in this SAP are summarized below. The methods by which each of these analyses is performed will be included in the SAP. The required analyses and target endpoints for the Slit Stent II include, but are not limited to, those listed below. If there are any discrepancies between the statistical analyses described in the SAP versus this protocol, the SAP will prevail. Tabulation of summary statistics, graphical presentations, and statistical analyses will be performed using SAS® and/or R software. All subjects who are enrolled in this study will be included in the safety analysis. All testing and confidence intervals will use a two-sided significance level of 5%.

Specific analyses for the six listed objectives are very similar to one another. Data will be summarized by treatment group (Slit Stent II or BIKA for DCR): counts and percentages for categorical variables, means and standard deviations for continuous variables. Additionally, 95% confidence intervals will be provided for each treatment group and for the difference between treatment groups. The confidence intervals for differences are keys to exhibiting the similarity between the Slit Stent II and the existing BIKA stent.

As this is a randomized experiment, control for pre-treatment variables is not necessary. However, a sensitivity analysis controlling for the baseline measurement of the outcome variable will be conducted. For example, post-surgery Lac-Q will be regressed on treatment and pre-surgery Lac-Q. If pre- and post-surgery measures are highly correlated, the confidence interval for the treatment effect will be narrower (more precise). If measurements are made at multiple post-surgery time-points, (generalized) linear mixed models will be used to estimate an overall (fixed) treatment effect while accounting for any correlation between measurements on the same person (random intercept).

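### The Lac-Q's eight-week recall at the day 5-14 visit covers mostly pre-operative days, so its effects should be reported by visit rather than pooled

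*Combined protocol and SAP*

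**What the plan says.** Appendix B reproduces the Lac-Q. The social-impact part asks "Which of these five statements is true about the tear duct problem overall in the last eight weeks", and the eye-symptom part tells the subject to "put a tick in the box next to the statement which best describes the situation over the last eight weeks".

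Section 9.0 sets the timing: "For the pre-op and all post op study visits, the Lac-Q Questionnaire will be administered by an interviewer". Section 9.4 fixes the first of these visits: "All subjects will be seen for a 1st post-operative visit 5-14 days after the DCR with intubation". It puts the second at day 30-120 and the last at month 5-7, "with the exact timing dependent on patient findings and surgeon discretion". The flow chart in Appendix D marks the Lac-Q at all three. Section 5.0 describes 2-4 months as the usual time of the second visit. The stent is removed at that visit (sections 8.2 and 9.4).

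No section changes the recall period for a post-operative visit. By contrast, the GBI in Appendix A was adapted to refer to the tear duct surgery, and the irritation question in Appendix C is anchored to surgery.

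Section 10.0 uses the Lac-Q as its worked example of baseline adjustment: "post-surgery Lac-Q will be regressed on treatment and pre-surgery Lac-Q". It then sends outcomes measured at several post-surgery times to a mixed model with a random intercept and one overall treatment effect. It mentions no visit term, no treatment-by-visit term and no exception for day 5-14. Section 10.5.2 names an analysis visit for the GBI; section 10.5.3 names none for the Lac-Q.

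**The concern.** A score taken 5 to 14 days after surgery, with an eight-week look-back, is labelled post-surgery but asks mainly about the pre-operative period. No stent had been placed on those days, so they carry neither a surgical benefit nor a difference between stents. If they enter the answers, they reduce both contrasts that section 4.0 wants from the Lac-Q under objectives 3 and 4: against no treatment effect and against control.

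Shrinkage toward zero is not cautious here. Section 10.0 relies on the intervals for differences to show that the two stents are similar, so dilution makes similarity look better supported than it is. Baseline adjustment does not repair this. Overlapping recall can itself raise the pre/post correlation and so narrow the interval around a shrunken estimate.

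The timing also matters. Section 3.3 names faster relief of tearing as a benefit, which is an early effect with the stent in place. Of the three Lac-Q visits, day 5-14 always overlaps the pre-operative period and the second visit can. Month 5-7 does not overlap but comes after stent removal.

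**Working it through.** **The plan's own figure.** Section 10.1 gives a margin of error of 0.57 SD for a difference of two means with 25 per arm. Check: t(0.975, 48 df) × √(2/25) = 0.569. This reproduces, and step 4 uses it.

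**1. Overlap.** Inputs: a window of 8 × 7 = 56 days (Appendix B) and the visit days in section 9.4. Pre-operative share o = max(0, 56 − visit day)/56.

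| Visit day | Calculation | Pre-operative share |
|---|---|---|
| 5 | 51/56 | 91% |
| 14 | 42/56 | 75% |
| 30 | 26/56 | 46% |
| 45 | 11/56 | 20% |
| 56 or later | 0/56 | 0% |

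Counting the day of surgery or of the visit differently moves the overlapping figures by less than 2 percentage points.

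**2. What pooling could do.** With three complete visits, each has one third of the weight in the overall effect. Assume that a share w of each answer is spread evenly over the 56 days and the rest reflects the post-operative state; w is not in the documents. If the true effect is constant and the second visit is at day 56 or later, the pooled estimate retains 1 − w × o₁/3:
- w = 0: 100%
- w = 0.5: 1 − 0.5 × 0.911/3 = 85% (day 5) to 1 − 0.5 × 0.750/3 = 88% (day 14)
- w = 1: 1 − 0.911/3 = 70% to 1 − 0.750/3 = 75%

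These figures show direction only and are not bounds. The social items are ticked if true at any time in the window, and the watery-eye item is an ordered frequency category. Neither is a daily average.

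**3. Why not simply drop day 5-14 and pool the other two visits.** Suppose the stent difference is D while the stent is in place and 0 at month 5-7, with the second visit at day 56 or later.
- Three-visit pool: (2 − w × o₁)/3. This is 67% of D at w = 0, 51-54% at w = 0.5 and 36-42% at w = 1.
- Two-visit pool: (1 + 0)/2 = 50% of D at every w.
- Break-even: w = 0.5/o₁, which is 0.55 (day 5) to 0.67 (day 14).

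With the second visit at day 30 (o₂ = 0.464), break-even is w = 1/(2o₁ − o₂), which is 0.74 to 0.97. Below these values, the two-visit pool dilutes an early effect more than the three-visit pool does.

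**4. Precision cost of reporting by visit.** The margin for three pooled visits is 0.569 × √((1 + 2r)/3), where r is an assumed within-person correlation:
- r = 0.3: 0.42 SD
- r = 0.7: 0.51 SD

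A single visit gives 0.57 SD.

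**The case against.** The strongest reply is that the consequence is limited. The only non-inferiority margin and power calculation concern the GBI (section 10.1), whose effectiveness parameter is the 1-4 month visit (section 10.5.2). There is no Lac-Q margin or decision rule. The overlap affects both randomised arms alike, so it does not favour either stent directly. Subjects may in practice answer for recent days. A second visit at the usual 2-4 months already gives a stent-in-place Lac-Q with essentially no overlap. Early tearing is also covered by GBI item 16, by tear lake height and by the subject's "report of their tearing symptoms since the surgery procedure". Finally, section 10.0 is a general summary that defers to a detailed SAP, which is not among the documents and would prevail.

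All of this stands, and it limits the point. It does not remove it: the other measures do not correct the Lac-Q estimate, and the stated default is a single pooled effect that includes day 5-14.

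A reader might infer three stronger things that the documents do not support:
- **That 75-91% measures the bias.** It is a share of calendar days; how subjects weight those days is unknown.
- **That the day 5-14 Lac-Q should be discarded and the rest pooled.** Step 3 of the working shows that this can dilute an early effect further.
- **That the trial's main effectiveness result is compromised.** The GBI items are tied to the surgery and have no eight-week window.

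A separate matter is the pain response "Pain or soreness, has used prescription eyedrops". Section 9.3.3 prescribes postoperative drops to every subject, so this response may raise postoperative scores in both arms. Reporting by visit does not resolve that.

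**Conclusion.** The point holds as a cheap improvement to the analysis. It follows from the text that 75% to 91% of the Lac-Q recall window is pre-operative at day 5-14, and 46% at a second visit on day 30. At 2-4 months and at month 5-7 the overlap is essentially nil. That day 5-14 would be pooled is the default reading of section 10.0; a later SAP could say otherwise.

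The direction of the effect, toward zero for both the change and the arm difference, rests on subjects answering at least partly for the whole window. Its size cannot be computed from the documents, and the retained-effect figures above depend on an assumed w and an assumed course of the true effect. The GBI endpoint and its power are not affected.

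**What to change.** In section 10.0 and the SAP, for the Lac-Q:

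1. Replace the single overall effect with a mixed model that has visit and treatment-by-visit terms. Report the arm difference and the change from baseline separately at each visit.
2. Base Lac-Q conclusions on the second visit (stent in place up to removal) and on month 5-7 (no overlap, but after removal). Do not merge them into one pooled effect, because that mixes stent-in and stent-out periods.
3. Keep day 5-14 as its own row, with a note that its recall window is mostly pre-operative.
4. Tabulate the day of the second visit by arm, so that any remaining overlap can be seen.
5. For early effect, summarise by arm the day 5-14 GBI and tear lake height. Add the since-surgery tearing report only if it is recorded in a form that can be summarised; section 9.4 gives it no response scale.

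This needs no new visits or data and leaves the published questionnaire unchanged. The price is precision: a margin of about 0.57 SD per visit instead of 0.42 to 0.51 SD for three pooled visits. The month 5-7 row also needs care, because section 9.4 expects some subjects not to travel, especially after successful surgery.
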